PAF patients, fulfilling the inclusion criteria will be recruited from Centre for Heart Rhythm Disorders (CHRD), Royal Adelaide Hospital (RAH), University of Adelaide and Cardiovascular Centre, Norwood (Professor [name]'s rooms). The participants (125 in each arm), will be randomized to intervention or control arm during the recruitment phase over a study period of 24 months. Participants will be risk profiled according to their age (30-50, 50-70, > 70 yrs.) and baseline central blood pressure (pre-HTN, HTN with or without end organ insult) into three groups. The control group will have conventional risk stratification as per brachial BP.

The following inclusion and exclusion criteria will be applied:

Inclusion Criteria

- 1. Age 20-80 years
- 2. Persistent and Paroxysmal AF patients
- 3. Able and willing to provide written informed consent

Protocol for HIGH IMPACT- AF study

Centre For Heart Rhythm Disorders, Royal Adelaide Hospital, University of Adelaide

Exclusion Criteria

- 1. Age <20years
- 2. Contraindications to exercise stress test (EST)
- 3. Pregnancy
- 4. Active malignancy or severe illness
- 5. Active Inflammatory disorder
- 6. Severe Aortopathy
- 7. Advanced valvular heart disease including aortic insufficiency (AI)
- 8. Constrictive or restrictive cardiomyopathy
- 9. Contraindications to non-contrast CMR (*only in selected patients scheduled for* *PVI*)

Withdrawal Criteria

Participants may withdraw at any time from the study. Patient will be excluded from the study if she will become pregnant during follow up.

D. STUDY DESIGN, TIME LINE AND INTERVENTIONS

It is a single centre, single blinded, prospective, randomised control study to collect and compare data to risk stratify our AF patients according to their aortic stiffness severity and central or peripheral blood pressure. Participants will be randomised to intervention or control group.

Intervention group will have their anti-hypertensive therapy titrated as per central blood pressure targets (Table-1), while the control group will have their brachial blood pressure treated as per current treatment guidelines (BP \leq 140/90 mmHg if risk of CVD is \leq 1% per year or 130/80mmHg if CVD risk is \geq 2% per year [21].

In addition, participants will be categorised according to their age (20-50yrs, 50-70yrs and >70yrs) and blood pressure into pre-HTN or HTN with or without end organ damage.

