Off note that the reported "normal range" of central blood pressure is estimated invasively while the participants are monitored in a controlled environment and under the effect of mild sedation. To prevent any harm to our study participants, we will take a holistic approach to risk stratify our patients while instigating treatment based on central or brachial pressures in order to avoid symptomatic hypotension along with drug side effects. The risk profiling will include age of the participants, aortic pulse wave velocity, baseline BP, degree of HTN induced end organ injury, BP response to exercise and central or brachial pressure indices including pulse pressure.

In case if patient has presenting BP characterised as grade II or higher HTN, a graduated approach will be adapted to lower the BP gradually by keeping an eye on the side effects of anti-HTN treatment.

CASP normal range						
Age (years)	Average (mmHg)	Minimum (mmHg)	Maximum (mmHg)			
20-30	101	90	112			
30-40	105	94	116			
40-50	108	97	119			
50-60	112	101	123			
60-70	115	104	126			
70-80	119	108	130			
80-90	122	111	133			

Table-1. Central Arterial Systolic Pressure (CASP) normal range as per age.

All AF patients will be assessed at baseline visits and at clinical follow-ups at RAH and Cardiovascular Centre, Norwood (Prof. [name]' rooms). Follow-up visits will be performed 3 monthly for the intervention group and six monthly for control as per treating electrophysiologist for 18-20 months (Tables 2 and 3). Participants will be risk stratified as per their central or brachial blood pressure indices into interventional and control group respectively.

The study will be approved by the ethics committee of RAH, University of Adelaide. Central blood pressure indices and carotid-femoral PWV analysis will be performed as per IMPULSE-AF validation study protocol. (CALHN Ethics and Research Committee Approval: R2010712, HREC Reference: HREC/16/RAH/269).

Table-2. Follow up and Investigations time line for Intervention Group (AFSS= AF symptom scale, CBP= central blood pressure, CPI= central pressure indices, EST= exercise stress test, PWV= pulse wave velocity, RFTs= Renal function test)								
0 months	3 months	6months	9months	12 months	15months	18-20 months		

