Demographics and cardiovascular (CV) risk profiling	CPI and PWV including lying and standing CBP	CPI and PWV including lying and standing CBP	CPI and PWV including lying and standing CBP	CPI and PWV including lying and standing CBP	CPI and PWV including lying and standing CBP	CPI and PWV including lyin and standing CBP		
*CPI and PWV including lying and standing CBP (Sphygmocor)	AFSS, RFTS	AFSS, RFTS	AFSS, RFTs	AFSS, RFTs	AFSS, RFTs	AFSS, RFTs		
Echo, EST, Holter 4-7 days, AFSS, Retinal examination, Serum and urinary analysis.	Holter 4-7 days	Holter 4-7 days	Echo, EST, Holter 4-7 days, Serum and urine analysis	Holter 4-7 days, Retinal examination	Holter 4-7 days	Echo, EST, Holter 4-7 day Retinal examination, Serum and uri analysis		

Tables to illustrate follow up and intervention time lines for two groups

*Offer treatment as per central BP targets. (Table-1).

Additional electro-anatomical mapping to estimate scar burden along with CMRI will be offered to patients listed for AF ablation. The CMR will be repeated after 12 months to assess AAD in a year as per IMPULSE AF protocol (CALHN Ethics and Research Committee Approval R2010712, HREC Reference: HREC/16/RAH/269)

Table-3. Follow up and Investigations time line for Control Group (AFSS= AF symptom scale, BBP= Brachial blood pressure, CBP= central blood pressure, CPI= central pressure indices, EST= exercise stress test, PWV= pulse wave velocity, RFTs= Renal function test)							
0 months	6months	11-13 months	18-20 months				
Demographics and cardiovascular risk profiling	BBP treatment targets as per current guidelines	BBP treatment targets as per current guidelines	BBP treatment targets as per current guidelines				
CPI, PWV (Sphygmocor) Brachial blood pressure (BBP) including lying and standing assessment, Retinal examination	Review for standard CV risk factor modification including AF and anti HTN treatment	Review for standard CV risk factor modification including AF and anti HTN treatment	Review for standard CV risk factor modification including AF and anti HTN treatment				

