Retinal photographs will be acquired from AF patients at baseline and during their follow up appointments yearly. Retinal vascular calibre will be measured from photographs using a validated computer program[22]. Retinal arteriolar and retinal venular calibre equivalents will be measured, and correlated with changes in central or peripheral blood pressures[22]. The acquisition of retinal image takes couple of minutes and it is a painless procedure that does not require any specific preparation.

[figure not shown]

Fig. 1. Sphygmocor applanation tonometry device (http://atcormedical.com/sphygmocor.html)

F. OUTCOMES OF THE STUDY

Primary outcomes to be evaluated include:

Association and Impact of central blood pressure control on AF outcomes (recurrence and AF burden).

Secondary Outcomes:

- Prevalence of central high blood pressure and aortic stiffness in AF patients with normal brachial BP.
- Association of brachial and central blood pressure indices including aortic stiffness to end organ insult and electro-anatomical remodeling of atria in AF patients.
- Correlating central blood pressure treatment target goals to proportionate decrease in events [Nephropathy (20% increase in ACR or 15-20% drop in estimated glomerular filtration rate (eGFR)), Left ventricular hypertrophy (LVH)/mass, LV diastolic dysfunction. Left atrial area and conduit vascular remodeling.
- Defining exaggerated BP response to exercise and postural change in our AF cohort and relating it with outcomes.
- > Number of anti-HTN required to achieve BP targets.
- Adverse events secondary to anti-HTN drugs including symptomatic postural BP drop of >20mmHg, acute kidney injury and electrolytes imbalance requiring hospitalization.

G. ETHICAL CONSIDERATIONS

Clinical Equipoise

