The study is a low risk, single blinded randomised trial to evaluate the impact and treatment of central high blood pressure on AF and CV outcomes. Central high blood pressure will be estimated by validated cuff based device (Sphygmocor) non-invasively. Vascular remodelling secondary to HTN, leads to aortic stiffness, which is a modifiable risk factor. At present, it is known that various anti-hypertensive agents can have significantly different effects on central aortic pressures despite similar brachial blood pressure valuation [23]. Agents such as inhibitors of the renin-angiotensin system and amlodipine could be started in individuals with increased aortic stiffness. As such, the investigators regarding the conduct of this study identify no specific ethical concerns.

Informed Consent

All patient participants will undergo a formal process of informed consent prior to study participation. Patients will be blinded with regard to their randomised group and will be treated for peripheral or central high blood pressure accordingly.

Drugs

No additional pharmaceuticals will be administered for the study protocol, with the exception of anti-HTN to achieve treatment target goals re central or brachial blood pressure. Side effects of anti HTN medication will be recorded by conventional clinical approach of reviewing the symptoms, documentation of postural drop in BP and monitoring of renal function tests during follow up or as required clinically.

Specific Safety Consideration

No significant increase in radiation dose is anticipated for the acquisition of electrophysiological data for the study because we are going to use 3D mapping to position the catheters in atria. The non-invasive assessment of blood pressure is not associated with any known risk. Retinal photography does not require any mydriatics.

H. ANALYSIS AND REPORTING OF RESULTS

Sample size calculation

Assuming the recurrence risk is 40% for AF in control, we estimate 90 patients in each group would give us 80% power to detect the 20% difference between groups at 5% significance level. Anticipating dropout rate of 28% over the course of the study, we would like to recruit 126 patients in each group.

Statistical Analysis

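### The only safety outcome counts drug-attributed events in a trial that blinds patients alone, and its postural drop has no stated measurement site and unequal schedules by arm

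*Protocol*

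**What the plan says.** Among the secondary outcomes in Section F there is one adverse-event outcome: "Adverse events secondary to anti-HTN drugs including symptomatic postural BP drop of >20mmHg, acute kidney injury and electrolytes imbalance requiring hospitalization". It does not say who decides that a drug caused the event, or whether the 20 mmHg drop is central or brachial.

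Section G (Drugs) describes how such events are captured: "Side effects of anti HTN medication will be recorded by conventional clinical approach of reviewing the symptoms, documentation of postural drop in BP", plus renal function tests during follow-up or when clinically needed. No blinded or independent assessor is named.

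On blinding, Section G (Informed Consent) says "Patients will be blinded with regard to their randomised group", and Section D calls the trial single blinded. Section D also says "Intervention group will have their anti-hypertensive therapy titrated as per central blood pressure targets", while control patients are treated to guideline brachial targets.

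On postural readings, Table 2 lists "CPI and PWV including lying and standing CBP" for the intervention arm at month 0 and at each of six follow-up visits. Table 3 lists "Brachial blood pressure (BBP) including lying and standing assessment, Retinal examination" for control at month 0. Its three later columns contain no lying and standing reading. Section E(a) limits central pressure in control patients to a single assessment at the first visit after randomisation.

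**The concern.** The trial tests more aggressive lowering of central pressure, and Section D names the harm it wants to prevent: treatment is to be individualised "in order to avoid symptomatic hypotension along with drug side effects". The Section F outcome is the only one that can show whether the central target causes more of that harm than usual care.

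Two features undermine it. First, a drug-causality judgement stands between an event and the count. A clinician who knows that a patient is on the experimental target may judge the same dizziness or creatinine rise differently from one who knows that the patient is on the guideline target. Second, the one quantified harm rests on a pressure whose site is not given, and the tables provide for different postural readings in the two arms. A difference in hypotension between arms, or the lack of one, could not then be put down to the treatment target.

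**Working it through.** The protocol gives no expected harm rate, so it has no figure to reproduce here. Its only computed figure is the sample size for AF recurrence, which does not bear on this point. The check is a side-by-side reading, followed by two illustrations on assumed values.

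**What each arm is scheduled to have**

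| | Intervention (Table 2) | Control (Table 3) |
|---|---|---|
| Follow-up visits | 6: months 3, 6, 9, 12, 15, 18-20 | 3: months 6, 11-13, 18-20 |
| Lying/standing at month 0 | central | brachial |
| Lying/standing at follow-up | central, all 6 visits | none listed |
| Blood tests at follow-up | renal function, all 6 visits | serum analysis at 11-13 and 18-20 months |

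The shared follow-up visits are about 6, 12 and 18-20 months. Neither table lists a standing brachial reading at any follow-up visit. Section G adds only an unscheduled record of postural drop.

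**Attribution.** Let *a*₁ and *a*₀ be the proportions of true events attributed to the drugs in the intervention and control arms. Then

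observed risk ratio = true risk ratio × (*a*₁ / *a*₀).

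The observed ratio equals the true one only if *a*₁ = *a*₀. Nothing in the protocol secures that equality, because titrating to an arm-specific target requires knowledge of the arm and no masked assessor is named. The documents give no values for *a*₁ or *a*₀.

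**Site of measurement (illustration; all inputs assumed).** Suppose that the brachial drop is normal with mean *m* and SD *s*, and that the central drop is the brachial drop divided by *k*. Then P(brachial > 20) = 1 − Φ((20 − *m*)/*s*) and P(central > 20) = 1 − Φ((20*k* − *m*)/*s*).

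| *m*, *s* (mmHg) | *k* | brachial | central | central/brachial |
|---|---|---|---|---|
| 5, 10 | 0.9 | 6.7% | 9.7% | 1.45 |
| 5, 10 | 1.1 | 6.7% | 4.5% | 0.67 |
| 5, 10 | 1.3 | 6.7% | 1.8% | 0.27 |
| 10, 12 | 0.9 | 20.2% | 25.2% | 1.25 |
| 10, 12 | 1.1 | 20.2% | 15.9% | 0.78 |
| 10, 12 | 1.3 | 20.2% | 9.1% | 0.45 |

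These are proportions of readings above 20 mmHg, not of symptomatic events, so they are not event rates. They show only that the site can move the count, in either direction.

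**Number of visits (illustration; *p* assumed).** If each follow-up visit independently detects an event with the same probability *p* in both arms, P(at least one) = 1 − (1 − *p*)^*k*, with *k* = 6 or 3.

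| *p* | 6 visits | 3 visits | ratio |
|---|---|---|---|
| 1% | 5.9% | 3.0% | 1.97 |
| 2% | 11.4% | 5.9% | 1.94 |
| 5% | 26.5% | 14.3% | 1.86 |
| 10% | 46.9% | 27.1% | 1.73 |

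With no true difference, visit-detected events would appear 1.7 to 2.0 times as often in the intervention arm. Removing the attribution filter alone would leave this imbalance in place. Because the site effect can go either way, the net direction cannot be settled from the documents.

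**The case against.** The best defence is that Section F names no site and Section G gives one recording method for both arms. A clinician documenting a postural drop in the conventional way might well use a brachial cuff in everyone. The central lying and standing readings in Table 2 may serve a different purpose: Aim 4 and the separate secondary outcome on exaggerated response to exercise and posture. This stands. A reader might infer from the tables that the 20 mmHg threshold is applied to central pressure in one arm and brachial pressure in the other throughout the trial. The documents do not say so, and after month 0 Table 3 schedules no postural reading to which a threshold could be applied. What remains is that the site is open and the scheduled readings differ.

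It is also fair that no text says who attributes events, and a masked procedure could sit in a document not shown. That treating clinicians do it is a strong inference, not a stated rule. But the restriction to drug-attributed events is itself written into the protocol. A later analysis plan cannot recover standing readings that were not taken, or events left unrecorded because they were judged unrelated.

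Finally, a reader might infer that symptomatic low pressure without a postural drop goes uncounted. The Section F list is open-ended and Section G reviews symptoms generally, so such a case may be recorded. It simply does not meet the one quantified hypotension criterion.

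**Conclusion.** The point holds as a weakness in how the protocol defines and schedules its only safety outcome. Counting only drug-attributed events, with patients alone blinded and treatment set by arm, leaves the comparison of harms open to bias. That rests on the inference that the attributing clinicians know the arm. The postural criterion has no stated site and the two schedules differ, so hypotension is not compared like for like.

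It would go too far to conclude that the comparison is biased in a known direction or by a known amount. The ratios above (0.27 to 1.45 for site, 1.7 to 2.0 for visit count) rest on assumed inputs, and the site figures concern readings, not symptomatic events. This is a secondary outcome and the primary analysis of AF recurrence and burden is untouched. The change should be made, because this outcome carries the trial's whole safety comparison.

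**What to change.** 1. In Section F, delete the restriction to events caused by antihypertensive drugs. Compare all symptomatic hypotension (postural or not), acute kidney injury and electrolyte events by randomised arm, whatever the attribution. Keep causality as a listing only.
2. Define the postural drop on lying and standing brachial pressure in both arms. Add that reading to Tables 2 and 3 at the shared visits (about 6, 12 and 18-20 months). Keep the central postural values as descriptive.
3. Base the between-arm comparison on the shared visits, because the intervention arm has six follow-up visits with renal tests at each and control has three, with serum analysis at two. Table 3 lists no blood test at 6 months, so for renal and electrolyte findings only the visits at about 12 and 18-20 months have a scheduled blood test in both arms.
4. State whether the hospitalisation condition applies to all three events or to electrolyte disturbance only.

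The cost is more than a change of wording. It takes edits to Section F and both tables, and a short cuff reading at three visits in each arm. Counts will include some events unrelated to the drugs. Those would not fall equally on the two arms if every visit were used, which is why the restriction to shared visits belongs with the first change.

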Echo, EST, Holter 4-7 days, AFSS, Serum and urine analysis. Conventional cardiovascular risk factor (CVRF) management as per treating physician	Holter 4-7 days, AFSS, Conventional CVRF management as per treating physician	Echo, EST, Holter 4-7 days, AFSS, Retinal examination, Serum and urine analysis. CVRF management as per treating Physician	Echo, EST, Holter 4-7 days, AFSS, Retinal examination, Serum and urine analysis. CVRF management as per treating Physician				

Additional electro-anatomical mapping to estimate scar burden along with CMRI will be offered to patients listed for AF ablation. The CMR will be repeated after 12 months to assess AAD in a year as per IMPULSE AF protocol (CALHN Ethics and Research Committee Approval R2010712)

Following assessments are standard for AF care and will be offered to all (control and intervention) participants.

a) Baseline Assessment

At baseline, following assessment will be performed for all participants:

- Weight and height recorded to calculate BMI.
- Demographics and conventional cardiovascular risk factors profiling by recording fasting glucose, lipid profile, age, gender, smoking history, systolic, diastolic, and pulse pressure.
- Brachial and aortic blood pressure (BP) assessment in a supine position after a resting period of 10 min by a mercury sphygmomanometer. Sphygmocor device will be applied to the right forearm over brachial artery to determine the central blood pressure indices as described previously (IMPULSE-AF protocol). Brachial blood pressure will be assessed by recording phase I and V of Korotkoff sounds to determine the brachial systolic and diastolic BP, respectively.
- Conventional 12-lead resting electrocardiograms (ECG) will be recorded and interpreted according to the Minnesota code (Mc).

Protocol for HIGH IMPACT- AF study

Centre For Heart Rhythm Disorders, Royal Adelaide Hospital, University of Adelaide

- Exercise stress test as per Bruce Protocol to assess exercise capacity.
- Blood will be drawn following a 12-hour fast to determine plasma lipids, fasting glucose, hs CRP and renal function.
- Trans-thoracic Echo (TTE) will be performed to assess Biventricular systolic and diastolic function along with left atrial size.
- 4 to 7days Holter monitoring to evaluate AF recurrence and arrhythmia burden

b) Exercise Tolerance Assessment

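### Postural drops and eGFR falls are looked for at six scheduled follow-ups in the intervention arm but at no more than three in control, so equal risk is likely to show as more harm on treatment

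*Protocol*

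**What the plan says.** Section D sets different visit intensities: "Follow-up visits will be performed 3 monthly for the intervention group and six monthly for control as per treating electrophysiologist for 18-20 months". What is done at each visit is listed in Tables 2 and 3.

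- **Intervention (Table 2).** Each of the six follow-up columns (3, 6, 9, 12, 15 and 18-20 months) has "CPI and PWV including lying and standing CBP" and renal function tests. The 9-month cell adds "Echo, EST, Holter 4-7 days, Serum and urine analysis", and that set is repeated at 18-20 months.
- **Control (Table 3).** The baseline column has "Brachial blood pressure (BBP) including lying and standing assessment, Retinal examination". No follow-up column mentions a lying/standing reading. At 6 months the tests are "Holter 4-7 days, AFSS, Conventional CVRF management as per treating physician", with no blood or urine test. At 11-13 and again at 18-20 months the entry is "Echo, EST, Holter 4-7 days, AFSS, Retinal examination, Serum and urine analysis. CVRF management as per treating Physician". Renal function tests are named in no control column.

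Section F makes two outcomes depend on these checks. One is the adverse-event outcome, "Adverse events secondary to anti-HTN drugs including symptomatic postural BP drop of >20mmHg, acute kidney injury and electrolytes imbalance requiring hospitalization". The other is "Nephropathy (20% increase in ACR or 15-20% drop in estimated glomerular filtration rate (eGFR". Neither has a stated assessment time. Section G (Drugs) says that side effects will be recorded through symptom review, postural drop and renal function at follow-up or when clinically needed, but sets no schedule.

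**The concern.** A transient finding that is noticed mainly because someone measured it accumulates with the number of measurements. If one arm is measured six times and the other two or three times, the share of patients with at least one finding will differ even when the underlying risk is the same.

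Here the extra measurements fall in the arm whose treatment is titrated to central pressure targets, so the distortion runs towards more apparent harm from the intervention. Tolerability is a central question for a strategy of tighter pressure control, so the harm comparison matters although it is secondary. A later analysis plan can choose which visits to use, but it cannot recover control measurements that were never taken.

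The eGFR criterion adds to the problem. It is written as a range, so a 17% fall can be counted as an event or not.

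**Working it through.** **1. Scheduled follow-up checks, counted from Tables 2 and 3**

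| Assessment | Intervention | Control |
|---|---|---|
| Lying/standing pressure | 6 | 0 |
| Renal bloods | 6 | 0 as named; 2 if serum analysis includes renal function |
| Either, if Section G is read as a check at every control visit | 6 | 3 |
| Urine (ACR) | 2 | 2 |
| Echo | 2 | 2 |

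The count of two for control renal bloods is itself generous. Renal function is listed for all participants at baseline (Section D), but the analytes under Serum and Urine Analysis in Section E do not include creatinine. For urine and echo, the last assessment is at 18-20 months in both arms. The mid-trial one is at 9 months against 11-13 months, a gap of 2 to 4 months.

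**2. Finding at least one event in k checks**

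Assume the same probability p per check in both arms and independent checks: P = 1 − (1 − p)^k. The protocol gives no value of p, so a range is shown.

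| p (assumed) | k = 6 | k = 3 | k = 2 | 6 vs 3 | 6 vs 2 |
|---|---|---|---|---|---|
| 0.02 | 11.4% | 5.9% | 4.0% | 1.9-fold | 2.9-fold |
| 0.05 | 26.5% | 14.3% | 9.8% | 1.9-fold | 2.7-fold |
| 0.10 | 46.9% | 27.1% | 19.0% | 1.7-fold | 2.5-fold |

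For p = 0.05: 1 − 0.95^6 = 0.265 and 1 − 0.95^3 = 0.143. With the 90 patients per group of Section H, that is about 24 against 13 patients (90 × 0.265 and 90 × 0.143). The chance of a nominally significant difference with no true effect is then about 53% for six against three checks.

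**3. eGFR drop in a patient with no true change**

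Let ln(eGFR) at each visit be a constant plus s·Z, with Z standard normal and s² = ln(1 + CV²). A drop of at least d from the single baseline is recorded when s(Z_j − Z_0) ≤ ln(1 − d). The probability of at least one in k tests is 1 − E[(1 − Φ(Z_0 + ln(1 − d)/s))^k]. The within-person CV is an assumption. For CV 6% and d = 15%, s = 0.0599 and ln(0.85)/s = −2.71.

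| CV (assumed) | Threshold | Six tests | Two tests |
|---|---|---|---|
| 5% | 15% | about 5% | 2.0% |
| 6% | 15% | 11.3% | 5.0% |
| 8% | 15% | about 26% | about 13% |
| 5% | 20% | about 0.4% | about 0.2% |
| 6% | 20% | 2.1% | 0.8% |

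With three control tests instead of two, the 6% CV and 15% threshold case becomes 11.3% against 6.9%. At 6% CV, the two ends of the written range change the intervention figure about five-fold (11.3 / 2.1 = 5.4).

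**4. The plan's own calculation**

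The only stated sample size (90 per group, 40% recurrence in control, 20-point difference, 80% power) is for AF recurrence. It is reproduced closely at 91 per group with a continuity correction (82 without). This point does not depend on it beyond borrowing the 90.

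**The case against.** Much of the case on the other side is sound, and it limits how far the point reaches.

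- **Six against zero is a count of table cells.** Section G applies symptom and postural review to both arms, and Table 3 has a treatment review at each of control's three follow-ups. Six against three is a fair reading. This stands, but it leaves a two-fold imbalance in checks.
- **The postural outcome is a symptomatic drop.** Symptoms may be reported without a scheduled measurement, which weakens the dependence on visit count. It does not remove it, because the 20 mmHg criterion still needs a measurement, and more visits give more chances to report.
- **Events requiring admission depend little on visit frequency.** The hospitalisation condition applies to electrolyte imbalance and may be read as covering kidney injury too. On that reading kidney injury is largely outside this point.
- **A reader might infer that the whole nephropathy outcome and the structural measures are biased.** The tables do not support that. ACR and echo are assessed twice in follow-up in both arms, with a shared 18-20 month visit. Only a mid-trial comparison would be confounded with time, and the protocol names no such comparison.
- **The at-least-once rule, the 5% and the CVs are assumptions.** Section F does not say that any visit counts, and an analysis plan may restrict the visits. Correlated or persistent findings would shrink the inflation. At 5% CV and a 20% threshold, the difference is under one patient per 90.
- **Closer monitoring of intensified treatment is legitimate.** Agreed. The difficulty lies in the between-arm comparison, not in the extra visits.

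**Conclusion.** The point holds for symptomatic postural drop, for kidney injury that does not require admission, and for the eGFR component of nephropathy. On every reading of the protocol, control has at most half the intervention arm's checks for these. Excess detection in the intervention arm is likely rather than certain. Its direction follows from the schedule, but its size rests on the assumed per-check probability, the assumed within-person CV, independence between checks, and counting a patient with any positive visit. Under those assumptions, six checks against three inflate the detected share by 1.7 to 1.9 times, and six against two by about 2.5 to 2.9 times.

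It would go too far to say that treatment will look more harmful on all renal and structural outcomes. It would also go too far to say that event calls will be made by unblinded staff: the protocol says that patients are blinded and does not say who classifies events. The 15-20% eGFR range is a separate imprecision, which makes the event rate depend on an unstated choice.

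**What to change.** 1. In Table 3, add a lying/standing brachial pressure and a named renal function test at control's existing 6, 11-13 and 18-20 month visits. Record the same brachial readings in the intervention arm at the matching visits, since Table 2 names the central pressure.
2. Base the between-arm comparison of postural and eGFR events on the common visits (6, about 12 and 18-20 months). Report findings from the extra intervention visits (3, 9 and 15 months) separately as safety data.
3. In Table 2, move only the echo, exercise test, serum and urine entries from 9 to 12 months. Leave the 9-month renal tests and pressures and the 12-month retinal examination where they are; exchanging whole columns would put the retinal examination out of step with control. Alternatively, keep the table and state that structural measures are compared at 18-20 months only.
4. Replace the eGFR range in the outcome definition with one pre-stated threshold, and also analyse eGFR as a continuous measure adjusted for baseline.

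The cost is a standing pressure reading and a routine blood test at visits that controls already attend, plus edits to two tables and one outcome definition. With equal numbers of checks at common times, the expected share detected under equal risk is the same in both arms.
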